7.5 SARS-CoV-2

For patients with suspected or confirmed SARS-CoV-2 infections, follow the dose modifications in Appendix E.

7.6 Pharmacokinetic and Anti-Drug Antibody Assessments

Patients will have PK and ADA blood samples collected at the times noted in the SOA.

Population PK and exploratory exposure-response analyses may be performed to characterize the relationships between dose and exposure and between exposure and efficacy and/or safety endpoints. If performed, results of population PK or exposure-response analyses will be reported separately from the Clinical Study Report.

The ADA testing will be performed using a validated ADA assay following tiered assay steps including Screening, confirmatory as well as titer determination. If ADA is confirmed, further analysis to profile immunogenicity of patritumab deruxtecan (e.g., neutralizing antibody assay) will be conducted. Serum concentrations of intact patritumab deruxtecan ADC, total anti-HER3 antibody and released payload MAAA-1181a may also be measured using the same ADA samples for purpose of ADA assessment.

CONFIDENTIAL

Instructions regarding sample collection, sample handling/processing and sample shipping are provided in the Laboratory Manual.

7.7 Biomarker Assessments

Tissue and blood will be collected for correlative testing prior to starting treatment.

7.7.1 Biomarker Tissue Samples

7.7.1.1 Fresh Biopsies

If medically feasible, all patients will have a pre-treatment biopsy. If it is not medically feasible to provide a pre-treatment biopsy, archival biopsy tissue that was taken 2 months prior to consent in Part A and Part B and 3 months prior to consent in Part Z should be provided. This sample should be obtained from a primary tumor or metastatic site, and not previously irradiated. All fresh biopsies will be processed according to the laboratory manual.

All patients in Part A will have an on-treatment biopsy in Cycle 2 between Days 1 and 7. Patients in Part B will have biopsies in Cycle 2 between Days 1 and 7 except for patients with HER3 expression who will follow a different schedule. The first 10 patients in Part B with HER3 expression will have the on-treatment biopsy in Cycle 1 between Days 15 and 21 and the next 10 patients with HER3 expression will have the on treatment biopsy in Cycle 2 between Days 1 and 7. The study team leader will track patient enrollment across multiple sites and track on-treatment biopsy collection. Once the 10th patient (Part B) on-treatment sample is collected and analyzed, an Investigator letter will be sent to the sites that the first 10 patients evaluable tumor requirement criteria have been met and sites are to proceed with the on-treatment biopsy schedule for patients 11-20.

All patients in Part Z will have an on-treatment biopsy in Cycle 2 between Days 1-7 unless not technically feasible or unsafe for the patient after discussion with the Medical Monitor.

Pre-treatment biopsies will be used to determine ER/PR/HER2/HER3 expression for Part A and Part B patients and HER2/HER3 expression for Part Z patients but will not be limited to markers mentioned here. Baseline, on-treatment, and EOT/PD samples will be used to evaluate RNA, protein and/or DNA for gene expression/mutation changes and exploratory protein biomarkers. The status of gene/protein expression including ER/PR/HER2/HER3 by IHC, HER2 amplification by fluorescence in situ hybridization (FISH), DNA/RNA sequencing, HER3 signaling analysis, DNA damaging marker such as γ H2AX, immune related markers such as PD-L1, PD-1 CD4, CD8, CD68, CD163 and novel DXd sensitivity and resistance markers may be tested to explore whether these are correlated with the response to treatment. The EOT/PD biopsies are optional for the patient.

If possible, sites should collect pre-treatment, on-treatment, and EOT/PD biopsies from the same tumor lesion. Accessible lesions are defined as tumor lesions that can be biopsied and that are amenable to repeat biopsy. Failure to obtain a sufficient tumor sample after making best efforts to biopsy the tumor will not be considered a protocol deviation.

Biopsies should be obtained through non-significant risk procedures. Sampling should be undertaken by experienced physicians in appropriate settings.

Instructions regarding sample collection, sample handling/storage/processing, and sample shipping are provided in the Laboratory Manual.

CONFIDENTIAL

7.7.2 Biomarker Blood Samples

Blood samples will be collected for exploratory analysis of circulating tumor DNA (ctDNA) and cell-free RNA (cfRNA) to explore changes in the molecular repertoire of HER3 genes at C1D1 and EOT. Blood samples will be analyzed using next-generation sequencing (NGS) of ctDNA. The clearance (disappearance) and emergence of new gene alterations before and following treatment will be explored.

Circulating tumor DNA (ctDNA) and cfRNA blood samples will be taken at the following time points for **Part A** patients:

- Cycle 1 Day 1 pre-dose for Part A patients
- Cycle 2 between Days 1 and 7 for Part A patients
- EOT visit or at disease progression for Part A and Part B patients

Circulating tumor DNA (ctDNA) blood samples will be taken at the following time points for **Part B** and **Part Z** patients:

- Cycle 1 Day 1 pre-dose for Part B and Part Z patients
- EOT visit or at disease progression for Part B and Part Z patients

Instructions regarding sample collection, sample handling/processing, and sample shipping are provided in the Laboratory Manual.

7.7.3 *BRCA1/BRCA2* mutational status

BRCA1/BRCA2 mutational status should be provided at Screening. If status is unknown, cannot be obtained from archival tissue or a blood sample, or patient refuses to be tested, they can still enroll in the study.

7.7.4 Biosample storage for future analysis

If the patient agrees, the remaining biomarker samples (tumor, blood or other specimen obtained in the study) may be stored for up to 15 years, and/or as per local regulation, and further analyzed to address scientific questions related to study drug(s) and/or relevant cancer indications.

8. DRUG FORMULATION, AVAILABILITY, ADMINISTRATION, AND TOXICITY INFORMATION

8.1 U3-1402 (patritumab deruxtecan)

Investigational Product	Dosage Form and Strength	Manufacturer
Patritumab deruxtecan	100 mg	Daiichi Sankyo

8.1.1 Labelling, Packaging, and Supply

Patritumab deruxtecan will be supplied by Daiichi Sankyo as vials in cartons labelled as “U3-1402”.

CONFIDENTIAL

The batch number of the study drug should be entered on the eCRF, if applicable.

The immediate packaging will contain a statement to conform with US Food and Drug Administration (FDA) Investigational New Drug (IND) requirements as follows: “Caution: New Drug - Limited by federal (or United States) law to investigational use.”

All study drugs must be kept in a secure, limited access place under appropriate storage conditions. Storage conditions for patritumab deruxtecan are included on the investigational product label and pharmacy manual.

Development Innovations must be granted access on reasonable request to check drug storage, dispensing procedures, and accountability records.

8.1.2 Preparation and Administration of Patritumab deruxtecan (U3-1402)

Patritumab deruxtecan (U3-1402) is administered as an IV infusion over approximately 90 minutes on Day 1 of Cycle 1. If there are no infusion-related reactions after this initial dose, then subsequent doses of patritumab deruxtecan will be infused over approximately 30 minutes on Day 1 of each subsequent cycle (Q3W).

Preparation and administration instructions will be provided in the pharmacy manual.

8.1.3 Precautions and Risks Associated with Patritumab deruxtecan

Precautions and risks are located in the IB.

8.2 Accountability for All Study Drugs

The Principal Investigator (or designee) is responsible for accountability of all used and unused study drug supplies at the site.

All study drug inventories must be made available for inspection by Development Innovations or its representatives and regulatory agency inspectors upon request.

Throughout the study and at its completion, Development Innovations Drug Accountability Record Form(s) will be completed by the site and sent to the Development Innovations Regulatory Department. Study drug supplies must not be destroyed unless prior approval has been granted by Development Innovations. Please contact Development Innovations regarding disposal of any study drug.

9. RESPONSE EVALUATIONS AND MEASUREMENTS

Response and progression will be evaluated in this study using RECIST Version 1.1 (see Appendix B). Lesions are either measurable or non-measurable according to the criteria. The term “evaluable” in reference to measurability will not be used, as it does not provide additional meaning or accuracy.

10. STATISTICAL CONSIDERATIONS

10.1 Statistical Design

This is a Phase II open-label study of patritumab deruxtecan in patients with MBC that will be conducted in 3 parts. Part A will enroll up to 60 patients with HER2- MBC. Part B will enroll an additional 20 patients into each of 2 subgroups that were defined from Part A (based on ER/PR/HER2/HER3 expression) following evaluation of biomarker expression in pre-treatment

CONFIDENTIAL

biopsy samples or in tissue from a biopsy done within 2 months prior to consent. A total of up to 40 patients will be enrolled into the following 2 Part B subgroups:

- MBC HR+, HER2-, regardless of HER3 expression, post-trastuzumab deruxtecan and/or sacituzumab govitecan therapy
- mTNBC, regardless of HER3 expression, post-sacituzumab govitecan and/or datopotamab deruxtecan therapy

The primary objective of this study is to evaluate overall response rate (ORR) and progression-free survival at 6 months (PFS-6) of single agent patritumab deruxtecan in patients with MBC.

10.2 Sample Size Considerations

Sixty patients will be enrolled into Part A, and the sizes of the biomarker expression-defined subgroups will not be restricted. Evaluation of biomarker expression-defined subgroups to carry forward into Part B will be based on evaluation of overall response rate (ORR), PFS-6, and results from correlative tests.

Patients in the subgroups from Part A that are expanded in Part B will be included in a combined subgroup for presentation (e.g., if 12 ER high/HER-3 high patients are treated in Part A, and that subgroup treats 20 additional patients in Part B, they would be added to the affiliated Part B subgroup for a total of 32 in analysis). Part Z will enroll an additional 21 patients with HER2+ MBC.

PFS-6 will be a binary endpoint with patients surviving progression-free for at least six month considered successes; otherwise, patients will be considered failures (including patients who withdraw from the study prior to six months). The ORR and six-month PFS will be presented with two-sided 95% confidence intervals (CIs) (calculated based on the Clopper-Pearson method). Table 5 below shows the precision of the estimates for the two endpoints across a range of sample sizes and ORR or PFS-6 rates.

Table 5 Projected CIs for ORR and PFS-6

Approximate ORR or PFS-6	n	Percentage (95% CI) [†]	Width of 95% CI [†]
0.20	20	0.20 (0.06, 0.44)	0.38
	25	0.20 (0.07, 0.41)	0.34
	30	0.20 (0.08, 0.39)	0.31
	35	0.20 (0.08, 0.37)	0.28
	40	0.20 (0.09, 0.36)	0.27
0.30	20	0.30 (0.12, 0.54)	0.42
	25	0.32 (0.15, 0.54)	0.39
	30	0.30 (0.15, 0.49)	0.35
	35	0.31 (0.17, 0.49)	0.32
	40	0.30 (0.17, 0.47)	0.30
0.40	20	0.40 (0.19, 0.64)	0.45
	25	0.40 (0.21, 0.61)	0.40

CONFIDENTIAL

Approximate ORR or PFS-6	n	Percentage (95% CI) [†]	Width of 95% CI [†]
	30	0.40 (0.23, 0.59)	0.37
	35	0.40 (0.24, 0.58)	0.34
	40	0.40 (0.25, 0.57)	0.32
0.50	20	0.50 (0.27, 0.73)	0.46
	25	0.52 (0.31, 0.72)	0.41
	30	0.50 (0.31, 0.69)	0.37
	35	0.51 (0.34, 0.69)	0.35
	40	0.50 (0.34, 0.66)	0.32

[†]Based on Clopper-Pearson.

10.3 Analysis Populations

The following analysis populations will be used:

- **Safety Analysis Set** will include all patients who received at least one dose of study treatment. For this study, the FAS and safety analysis set are identical.
- **Full Analysis Set (FAS)** will be comprised of all patients who received at least one dose of study treatment. For this study, the FAS and Safety Analysis Set are identical.

10.4 Data Analysis

Descriptive statistics, including mean, median, standard deviations, and ranges for all continuous measures, will be tabulated and reported. Percentages and frequencies for all categorical measures will also be presented. Time to event endpoints will be reported using Kaplan-Meier estimates, with 95% CIs for median time to event.

10.4.1 Demographics and Baseline Characteristics

Demographic and baseline disease characteristics will be summarized. Data to be tabulated will include demographic features such as age, sex and race, as well as disease-specific characteristics.

The number and percentages of patients who were screened, enrolled, treated, and discontinued the treatment/study for any reasons will be presented overall and also by biomarker-defined subgroups.

10.4.2 Efficacy Analysis

All efficacy analyses will be performed using the Full Analysis Set. Results will be presented overall and by biomarker-defined subgroup.

- **Objective Response Rate (ORR)**, defined as the proportion of patients with confirmed CR or PR (i.e., confirmation at least 4 weeks apart) according to RECIST Version 1.1 criteria (see Appendix B). Patients without a post-baseline tumor assessment will be classed as not evaluable (NE) and considered as non-responders.

CONFIDENTIAL

- Clinical Benefit Rate (CBR), defined as the proportion of patients with CR, PR or best overall response of SD for ≥ 6 months according to the RECIST v 1.1 criteria.
- Progression Free Survival (PFS) is defined as the time from start of study treatment to the date of event defined as the first documented radiological progression or death due to any cause. If a patient has not had an event, PFS is censored at the date of last adequate tumor assessment.
- Six-month PFS (PFS-6) rate is defined as the proportion of patients who survive progression-free for at least 6 months. Patients who discontinue the study prior to 6 months or do not have post-6 months tumor evaluations will be considered failures.
- Duration of response (DOR) is defined as the duration from the first documented response to the date of progression or death due to any cause. In case a patient does not have progression or die, DoR is censored at the date of last adequate tumor assessment (defined as an assessment of CR, PR or SD). Duration of response analysis will include only responders.

For ORR and PFS-6, estimates and the associated 95% CIs (based on the Clopper-Pearson method) in each biomarker-defined subgroup will be calculated.^f

For PFS, Kaplan-Meier curves will be generated, and the median time to event and the associated 95% CIs will be provided.

For DoR, Kaplan-Meier estimates will be generated and descriptive statistics (e.g., number of patients ongoing at time of cutoff, the number of patients with DoR ≥ 6 months) will be provided.

10.4.3 Safety Analysis

All safety endpoints, including laboratory results, vital signs, and ECG findings, will be summarized for patients in the Safety Analysis Set.

Adverse Events

Safety will be assessed through the analysis of the reported incidence of treatment-emergent AEs. Treatment-emergent AEs are those with an onset on or after the initiation of therapy up to 40 days (+ 7 days) after last day of treatment and will be graded according to NCI CTCAE Version 5.0. Serious adverse events starting or worsening after the on-treatment period, if reported as related to the study treatment, are also TEAEs. The AE summary will include only TEAEs.

The AEs will be coded using the current version of Medical Dictionary for Regulatory Activities (MedDRA; <https://www.meddra.org/about-meddra/>) and summarized using system organ class and preferred term overall and by biomarker-defined subgroup for all patients in the Safety Analysis Set. In addition, summaries of SAEs, AEs leading to treatment discontinuation, AEs by maximum NCI CTCAE grade, and AEs related to study treatment will also be presented overall and by biomarker-defined subgroup.

Clinical Laboratory Tests

Descriptive statistics will be provided for clinical laboratory test results (hematology and chemistry) and changes from baseline by scheduled time of evaluation, including the EOT visit.

CONFIDENTIAL

Abnormal laboratory results will be graded according to NCI CTCAE Version 5.0, if applicable. A shift table, presenting the 2-way frequency tabulation for baseline and the worst on-treatment value according to the NCI CTCAE grade, will be provided for clinical laboratory tests. Abnormal clinical laboratory test results \geq Grade 3 will be listed.

Concomitant medications will be coded using the World Health Organization Drug Dictionary (WHO DD; <https://www.who-umc.org/>), and they will be listed and summarized by overall and by biomarker-defined subgroup.

Vital Signs

Descriptive statistics will be provided for the vital sign measurements and changes from baseline by scheduled time of evaluation, including the EOT visit.

Electrocardiogram Analyses

Descriptive statistics will be provided for ECG parameters and changes from baseline, including the EOT visit. In addition, the number and percentage of patients meeting the following criteria will be tabulated for QT and QTcF: ≤ 450 msec, >450 to ≤ 480 msec, >480 msec to ≤ 500 msec, and >500 msec, and change from baseline ≥ 30 msec and ≥ 60 msec.

The QT intervals will be corrected for heart rate by Fridericia's formula ($QTcF = QT/[RR]^{1/3}$).

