Forty-six (31.9%) of the 144 treated patients had a treatment-emergent serious adverse event (SAE), including 31 (21.5%) patients with study drug-related SAEs. The most common SAEs reported in more than 1 patient, in descending order of frequency, included platelet count decreased (8 [5.6%] patients); vomiting (6 [4.2%] patients); decreased appetite (5 [3.5%] patients); nausea and thrombocytopenia (4 [2.8%] patients each); pneumonitis (3 [2.1%] patients); and febrile neutropenia, mental status changes, and urinary tract infection (2 [1.4%] patients each).

Treatment-emergent AEs were associated with a dose interruption in 68 (47.2%) patients and a dose reduction in 22 (15.3%) patients. Twelve (8.3%) patients discontinued study drug due to a TEAE.

Ten (6.9%) of the 144 treated patients experienced a potential interstitial lung disease (ILD) event (1 per patient) requiring ILD adjudication as of the data cut-off date, including 6 (4.2%) patients with pneumonitis (3 Grade 2 and 3 Grade 3), and 4 (2.8%) patients (1 patient each) with ILD (Grade 2), radiation pneumonitis (Grade 3), radiation fibrosis-lung (Grade 1), and respiratory failure (Grade 2). Treatment-emergent AEs in 7 of the above 10 patients (6 pneumonitis and 1 ILD) were considered as related to patritumab deruxtecan by the Investigators.

CONFIDENTIAL

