1.2 Potential Risks and Benefits of the Treatment Regimen

Patritumab deruxtecan is being developed for the treatment of HER3-expressing malignant tumors. The product is in the early stages of development.

Nonclinical studies have demonstrated the antitumor activity of patritumab deruxtecan in HER3 tumor-bearing mouse models. Thus, patritumab deruxtecan is hypothesized to demonstrate efficacy in treating HER3-expressing tumors in patients.

Based on the preliminary clinical safety data from the ongoing patritumab deruxtecan studies, nausea, decreased appetite, platelet count decreased/thrombocytopenia, white blood cell count decreased/leukopenia, neutrophil count decreased/neutropenia, vomiting, anemia, diarrhea, fatigue, malaise, stomatitis, constipation, ALT increased, AST increased, and alopecia are identified risks and will continue to be closely monitored and evaluated in the patritumab deruxtecan clinical development program.

Based on clinical data and safety information available as of the 05 August 2019 data cut-off, ILD/pneumonitis was added as an adverse drug reaction associated with the use of patritumab

CONFIDENTIAL

deruxtecan and considered an important identified risk. The reported ILD events were generally manageable via close monitoring and by following the ILD management plan in the protocol.

In conclusion, based on the efficacy and safety data from the nonclinical studies and the preliminary clinical safety data from ongoing studies, the benefit/risk balance supports continued clinical development of patritumab deruxtecan. For more information on the non-clinical and clinical studies, see the current patritumab deruxtecan Investigator’s Brochure (IB).

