11.1.5 Recording and Reporting of Adverse Events

Recording of Adverse Events

All AEs of any patient during the course of the research study will be recorded in the eCRF, and the Investigator will give his or her opinion as to the relationship of the AE to the study drug treatment (i.e., whether the event is related or unrelated to study drug administration).

All AEs should be documented. A description of the event, including its date of onset and resolution, whether it constitutes an SAE or not, any action taken (e.g., changes to study treatment), and outcome, should be provided, along with the Investigator's assessment of causality (i.e., the relationship to the study treatment[s]). For an AE to be a suspected treatment-related event, there should be at least a reasonable possibility of a causal relationship between the protocol treatment and the AE. Adverse events will be graded according to the NCI CTCAE Version 5.0, and changes will be documented.

If the AE is serious, it should be reported immediately to Development Innovations Safety Department. Other untoward events occurring in the framework of a clinical study are to be recorded as AEs (i.e., AEs that occur prior to assignment of study treatment that are related to a protocol-mandated intervention, including invasive procedures such as biopsies, medication washout, or no treatment run-in).

Any clinically significant signs and symptoms, abnormal test findings, changes in physical examination, hypersensitivity, and other measurements that occur will be reported as AEs and collected on the relevant eCRF screen.

Test findings will be reported as an AE if: the test result requires an adjustment in the study drug(s) or discontinuation of treatment and/or test findings require additional testing or surgical intervention, a test result or finding is associated with accompanying symptoms, or a test result is considered to be an AE by the Investigator.

Reporting Period for Adverse Events

All AEs, regardless of seriousness or relationship to patritumab deruxtecan treatment (called study treatment), spanning from the start of study treatment until 40 calendar days (+7 days) after discontinuation or completion of study treatment as defined by the clinical study for that patient

CONFIDENTIAL

after his/her last dose of study drug, are to be recorded on the corresponding screen(s) included in the eCRF.

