All AEs resulting in discontinuation from the study should be followed until resolution or stabilization. All new AEs occurring during this period must be reported and followed until resolution unless, in the opinion of the Investigator, the AE or laboratory abnormality/ies is/are not likely to improve because of the underlying disease. In this case, the Investigator must record his or her reasoning for this decision in the patient's medical record.

After 40 days after completion of protocol-specific treatment or discontinuation, only AEs, SAEs, or deaths assessed by the Investigator as treatment-related are to be reported.

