11.4 Protocol-Defined Adverse Events of Special Interest

For the patritumab deruxtecan clinical program, based on the available pre-clinical data, review of the cumulative literature, reported toxicities for the same class of agents and biological plausibility, the following events are considered to be AESIs, and will need to be reported expeditiously (see Section 11.1.5). These events include the following:

- Interstitial lung disease/pneumonitis
- Elevations of aminotransferases and bilirubin suggestive of Potential Hy's Law

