11.4.1 Interstitial Lung Disease Adjudication Committee

An independent ILD Adjudication Committee for patritumab deruxtecan is responsible for reviewing all cases of potential ILD/pneumonitis. To ensure adequate and relevant independent evaluation, systematic additional data collection will be conducted for all cases that will be

CONFIDENTIAL

brought for adjudication. This data collection will be triggered for adverse events reported using MedDRA preferred terms (PTs) from the current ILD Standard MedDRA Query (SMQ) and the PTs of acute respiratory failure and respiratory failure.

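### Section 10.4.3 may omit late, related, non-serious ILD and plans no single ILD summary; non-serious ILD also has no stated site reporting time

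*Combined protocol and SAP*

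**What the plan says.** **Status of the risk.** Section 1.2 records ILD/pneumonitis as an adverse reaction to patritumab "deruxtecan and considered an important identified risk". Section 11.4 lists it as one of two AESIs.

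**What is counted.** Section 10.4.3 closes the treatment-emergent window 40 (+7) days after the last day of treatment. It then adds: "Serious adverse events starting or worsening after the on-treatment period, if reported as related to the study treatment, are also TEAEs". The adverse-event summary is restricted to TEAEs. Events are "summarized using system organ class and preferred term overall and by biomarker-defined subgroup", with further summaries of SAEs, events leading to discontinuation, maximum grade and related events. The section does not mention AESIs, ILD as a group, or adjudicated ILD.

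**What is collected.** After day 40, Section 11.1.5 says "only AEs, SAEs, or deaths assessed by the Investigator as treatment-related are to be reported", and Section 11.2.1 sends related events to the Sponsor. Neither limits this to serious events.

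**Adjudication.** Under Section 11.4.1 an independent committee "is responsible for reviewing all cases of potential ILD/pneumonitis". Extra data collection is triggered by a defined term set: the ILD SMQ plus two respiratory failure terms.

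**Reporting speed.** Section 11.4 says AESIs "will need to be reported expeditiously (see Section 11.1.5"), with no seriousness limit. The section it points to says: "If the AE is serious, it should be reported immediately to Development Innovations Safety Department". Section 11.4.2 gives hepatic AESIs a 24-hour rule whether or not they are serious. Section 11.4.1 has no equivalent for ILD.

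**The concern.** Safety is the first secondary objective, and ILD is the toxicity for which the protocol sets up its own adjudication. A reader of the study report will want one figure: how many patients had ILD, at what grade, and how many were judged drug-related. The plan gathers the data for that figure but does not define it.

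Two matters bear on the analysis. The TEAE definition is narrower than the collection rule, so one kind of ILD event can be recorded and then left out of every planned summary. The grouped and adjudicated views that Section 11.4.1 makes possible are also not among the stated outputs. A third matter is separate and concerns timeliness, not counting: the cross-reference for expeditious reporting leads to no stated site timeline for a non-serious ILD event.

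**Working it through.** **1. The plan's own figures.** Section 1.1.3 reports from J101: "Ten (6.9%) of the 144 treated patients experienced a potential interstitial lung disease (ILD) event", one per patient. These reproduce:
- All potential ILD: 10/144 = 6.9%.
- Pneumonitis: 6/144 = 4.2%.
- The four other events (ILD, radiation pneumonitis, radiation fibrosis-lung, respiratory failure, one patient each): 4/144 = 2.8%.
- Pneumonitis listed as an SAE: 3/144 = 2.1%.
- Considered related by investigators: 7 (6 pneumonitis and 1 ILD), so 7/144 = 4.9%.

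Planned enrolment is 60 + 40 + 21 = 121.

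**2. Which ILD events are lost by the TEAE rule.**

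| ILD event | Collected? | In the AE summary? |
|---|---|---|
| Starts within 40 (+7) days, any seriousness | Yes | Yes |
| Starts later, related, serious | Yes | Yes |
| Starts later, related, non-serious | Yes | **No** |
| Starts later, unrelated | No | No |

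Only the third row is a gap. The rule in Section 6.2.1 that all ILD is followed to resolution does not widen it, because TEAE status depends on onset. An event that starts inside the window and runs on for months is already counted.

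**3. Size of that gap.** Assumptions: the J101 related rate carries over, although J101 used other doses; the late-onset share L is the same for serious and non-serious events; and L lies between 0% and 30%, since the documents give no value.

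Expected related ILD = 121 × 7/144 = 5.9 patients.

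Non-serious share of related ILD: 3 of the 6 pneumonitis cases were SAEs, and the seriousness of the single ILD case is not given. The share is therefore 3/7 to 4/7.

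Expected patients omitted = 121 × 7/144 × (3/7 to 4/7) × L = (2.52 to 3.36) × L.

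| L (assumed) | Patients omitted | Share of related ILD |
|---|---|---|
| 0% | 0 | 0% |
| 10% | 0.25 to 0.34 | 4.3% to 5.7% |
| 20% | 0.50 to 0.67 | 8.6% to 11.4% |
| 30% | 0.76 to 1.01 | 12.9% to 17.1% |

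**4. Grouping.** The ten J101 events fell under five terms, the largest with six. Each term gets its own row in a preferred-term table, so splitting removes no event. With one event per patient the rows sum to the patient count. If a patient has two ILD terms, the rows no longer give the number of patients with any ILD, or their worst grade. No row shows the committee's decision.

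**5. Reporting route.** The chain for a non-serious ILD runs from Section 11.4 (expeditious reporting required) to Section 11.1.5 (immediate reporting for serious events only). The 24-hour rule in Section 11.2 is for SAEs, and the one in Section 11.4.2 is for hepatic AESIs. Section 11.5 has a 15-day step for AESIs, but it runs from sponsor to funding partner. No site timeline results. In J101 the four single-patient events may or may not have been SAEs, so SAEs numbered 3 to 7 of the 10 potential events, and 10 − (3 to 7) = 3 to 7 were non-serious.

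**The case against.** The best defence is that little is lost. The gap needs an event that is late, related and non-serious, and the documents do not show that any will occur. Every preferred term is tabulated. Patients who stop treatment for ILD also enter the discontinuation summary, and Table 4 requires stopping at Grade 2 and above. Adjudication might lower the investigator count as easily as raise it. The committee is described as serving the compound, its charter is not supplied, and its results may be used elsewhere. This is a descriptive, single-arm phase II study.

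Most of that stands, and it rules out several stronger readings:
- A reader might infer that ILD will certainly be under-counted. The late-onset share is not given, so only a possible omission can be claimed.
- A reader might set 4.2% beside 6.9% and infer a 40% shortfall (1 − 6/10). The 6.9% is potential, unadjudicated ILD, not a true rate, and all five terms are shown. For related events the comparison is 6 against 7 of 144 (4.2% and 4.9%), or 5.0 against 5.9 patients at 121.
- A reader might infer that non-serious ILD has no expedited requirement. Section 11.4 imposes one; what is missing is the site timeline.
- A reader might infer that all Part B patients have had a deruxtecan conjugate. Prior sacituzumab govitecan alone qualifies. Only Part Z requires prior trastuzumab deruxtecan, and Part A excludes such exposure.

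The defence does not answer the mismatch between collection and the TEAE definition. The discontinuation summary cannot catch an event that starts after treatment has ended. Nor does the defence explain why a defined term set and committee have no stated output.

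**Conclusion.** The point holds in a limited form. Followed exactly, Section 10.4.3 leaves a late, related, non-serious ILD out of every planned adverse-event summary, although the protocol collects it. The effect is probably small: about 0 to 1 of 5.9 expected related cases at 121 patients, given the J101 rate and an assumed late-onset share of 0% to 30%. The true size cannot be fixed from the documents.

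The lack of a stated grouped or adjudicated ILD summary is the more useful finding. It does not show a bias in either direction; it leaves the ILD result undefined. The cross-reference from Section 11.4 to Section 11.1.5 is a separate inconsistency that affects how soon non-serious cases are known, not how many are counted. None of this affects the efficacy analyses. It is worth correcting because the risk is a named one and the correction is cheap.

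**What to change.** In Section 10.4.3:
- Extend the sentence on events after the window from related SAEs to related SAEs and related AESIs of any seriousness, or list such late AESIs separately.
- Add one ILD/pneumonitis composite, counted per patient, using the term set already in Section 11.4.1. Show it by worst grade, as investigator-reported and as adjudicated.

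Separately, reconcile Sections 11.1.5, 11.4 and 11.4.2 so that non-serious ILD has a stated site reporting time.

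The cost is one reworded sentence, one table and one corrected cross-reference. The committee, term set and data collection already exist. The downside is a possibly slightly higher reported ILD rate and a few more expedited forms. No treatment rule changes.
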